5.2 Inclusion Criteria

The subject must meet the following criteria to be eligible for the study:

1. Signed and dated informed consent to participate in the study.
2. Men or women aged 20 years or older of Chinese origin.
3. Subjects willing to abstain from any other facial plastic surgical or cosmetic procedures below the level of the lower orbital rim for the duration of the study of a maximum of 31 days(e.g., laser or chemical resurfacing, needling, facelift, radiofrequency, etc.).

2017-04-13 06:29

Effective date:

4. Intent to undergo correction of both NLFs [REDACTED]

5.3 Exclusion Criteria

The presence of any of the following exclusion criteria will exclude a subject from enrolment in the study:

[REDACTED]

[REDACTED]

[REDACTED]

4. Previous tissue revitalization treatment with laser or light, mesotherapy, radiofrequency, ultrasound, cryotherapy, chemical peeling or dermabrasion in the midface within 6 months before treatment.

[REDACTED]

[REDACTED]

6. Previous tissue augmentation therapy or contouring with any permanent (non-biodegradable) or semi-permanent filler, autologous fat, lifting threads or permanent implant below the level of the lower orbital rim.

7. Previous use of any hyaluronic acid based or collagen based biodegradable facial tissue augmentation therapy below the level of the lower orbital rim within 12 months before treatment.

[REDACTED]

[REDACTED]

[REDACTED]

10. Scars or deformities, active skin disease, inflammation or related conditions, such as infection, perioral dermatitis, seborrheic eczema, rosacea, acne psoriasis and herpes zoster near or in the area to be treated.

[REDACTED]

[REDACTED]

[REDACTED]

[REDACTED]

[REDACTED]

Version: 1.0

	Title 43TW1628 Clinical Study Protocol	Doc id MA-34273
--	--	---------------------------

2017-04-13 06:29

Effective date:

Effective

Version: 1.0

20. Other condition preventing the subject from entering the study in the Investigator's opinion, e.g. subjects not likely to avoid other facial cosmetic treatments, subjects anticipated to be unreliable, unavailable or incapable of understanding the study assessments or having unrealistic expectations of the treatment result.

5.4 Screening and Subject Numbers

Each screened subject will be assigned a screening number consisting of "S" and the site number followed by a consecutive number starting with 01 at each site, e.g. S101, S102. The screening number shall be listed on a subject screening and inclusion log.

A "screening failure" is defined as a subject who does not fulfil the eligibility criteria. For screening failures, the eCRF screening visit shall be completed to an extent that makes it clear which assessments have been made and the reason why the subject did not fulfil the eligibility criteria. The reason for excluding a subject from entering the study shall also be specified in the subject screening and inclusion log.

When the Investigator has confirmed that all inclusion criteria and no exclusion criteria are met, each enrolled subject will be assigned a subject number by the eCRF consisting of the site number followed by a consecutive number starting with 01 at each site, e.g. 101, 102.

The screening number, subject number, subject name, and other information sufficient to link the eCRF to the medical records (e.g. national identification number, chart number, etc.) shall be recorded on a subject identification list. The subject identification list shall only be available at the site, both throughout and after the study.

 GALDERMA	Title 43TW1628 Clinical Study Protocol	Doc id MA-34273
--	--	---------------------------

5.5 Withdrawal of Subjects

Each subject shall be advised in the Informed Consent Form that the subject has the right to withdraw from the study at any time, for any reason, without prejudice. Subjects may also be discontinued from this study if the Investigator determines that it is in the subject's best interest to do so, and may be withdrawn at the Investigator's discretion at any time.

[REDACTED]

- [REDACTED]
- [REDACTED]
- [REDACTED]
- [REDACTED]
- [REDACTED]

The reason and date for withdrawal shall be documented in the eCRF. When possible, an explanatory comment shall be added in the study termination module/pages to further explain the reason for withdrawal. If withdrawal of a subject occurs during a regular study visit, the eCRF for that specific visit shall be completed as far as possible together with the study termination eCRF module.

If withdrawal of a subject occurs between regular study visits the subject should when possible (irrespective of the reason for withdrawal) be scheduled for a termination visit to document subject outcome for the primary and secondary endpoints. In these cases the eCRF for the early termination visit should be completed. The subject will need to follow the same requirements for the visit at day 15.

If a subject is withdrawn from the study, all data collected until the time of withdrawal will be used in the analyses.

A withdrawn or discontinued subject must not be replaced or re-entered into the study.

If an AE which, according to the Investigator's assessment, is related to the use of any of the study products and is still ongoing at the time of the withdrawal, the Investigator shall follow-up the subject until the AE resolves or is assessed by the Investigator to be "chronic" or "stable". Follow-up information for at least three months shall be provided to the Sponsor.

6 Study Products

The term "study products" refers to Perlane-Lido and Perlane.

 GALDERMA	Title 43TW1628 Clinical Study Protocol	Doc id MA-34273
--	--	---------------------------

6.1 Investigational Product

Perlane-Lido is a sterilized injectable gel consisting of stabilized HA of non-animal origin with concentration 20 mg/mL in phosphate buffered saline with lidocaine hydrochloride 3 mg/mL. The gel is transparent and colorless. The product is supplied in single use sterile syringes with a luer-lock fitting. Each syringe contains 1 mL gel. The syringe is labeled and packaged in a blister, with two 29G thin walled (TW) \times $\frac{1}{2}$ " needles. The Investigational Product is a commercial product intended for the Taiwan market. An Instruction for Use (IFU) is included in the carton.

6.2 Reference Product

Perlane is a sterilized injectable gel consisting of stabilized HA of non-animal origin with concentration 20 mg/mL in phosphate buffered saline. The gel is transparent and colorless. The product is supplied in single use sterile syringes with a luer-lock fitting. Each syringe contains 1 mL gel. The syringe is labeled and packaged in a blister with two 29G thin walled (TW) \times $\frac{1}{2}$ " needles. The Reference Product is a commercial product intended for the Taiwan market. An Instruction for Use (IFU) is included in the carton.

6.3 Additional Products and Material

Perlane-Lido and Perlane will be supplied by the Sponsor. Any other materials will be supplied by the site.

6.4 Packaging, Labelling and Storage

6.5 Product accountability

The study product will be released to the PI or his/her authorised designee after study approvals have been received from the IEC/IRB and the CTA has been signed by all parties.

 GALDERMA	Title 43TW1628 Clinical Study Protocol	Doc id MA-34273
--	--	---------------------------

Effective date: 2017-04-13 06:29

The PI must ensure that the study product is kept in a secure location, with access limited to those authorised by the PI.

The study product must be traceable from the manufacturer to its use in subjects until return or disposal. It is therefore important that the PI maintains accurate product accountability records, i.e. documentation of the physical location of all study product, deliveries, and return of study product between the Sponsor or a third-party vendor and the PI, and documentation of administration of product to the subject. A shipping record shall be kept of all study products received from the Sponsor; including the product name, date received, batch number, expiration date, and amount received. In addition, dispensing logs shall be maintained including the product name, dispense date, the number of syringes used, the number of syringes left in stock, and the subject receiving study product. A log for accountability procedure is provided by the Sponsor.

When the study is completed, all unused or expired study product at each study site shall be returned to the Sponsor or a third-party vendor for destruction. Any malfunctioning study products shall be reported as described in Section 8.5.3.

Product deliberately or accidentally destroyed during shipment or at a study site shall be accounted for and documented. Used syringes, disposable needle, and any opened unused material must be discarded immediately after the treatment session and must not be reused due to risk for contamination of the unused material and the associated risks including infections according to standard procedures at the site. Disposal of hazardous material, i.e. syringes and needles must conform to applicable laws and regulations. The study product must not be used outside the study.

6.6 Treatment

[REDACTED]

[REDACTED]

[REDACTED]

[REDACTED]

[REDACTED]

[REDACTED]

Version: 1.0

Effective date: 2017-04-13 06:29

Effective

Version: 1.0

	Title 43TW1628 Clinical Study Protocol	Doc id MA-34273
--	--	---------------------------

2017-04-13 06:29

Effective date:

Effective

Version: 1.0

6.6.6 Treatment compliance

The treatment is an implant administered by the Treating Investigator and the details of the administration are recorded in the eCRF. No other measurements of treatment compliance will be made.

7 Pain Assessments

7.1 Pain assessment by Visual Analogue Scale (VAS)

The VAS is a subjective scale to measure pain intensity. The subject shall be instructed to put a vertical mark, approximating the pain experienced during the procedure, on a 100 mm horizontal line labelled "no pain" at the left end and "the worst pain you can imagine" at the right end. The distance in mm from the left end (no pain) to the subject's VAS mark shall be measured with a standard ruler. Each NLF will be evaluated independently.

Subjects will evaluate injection site pain for each side of the face at the time of injection (before massaging) and at 15, 30, 45, and 60 minutes post-treatment by completing a VAS.

Visual Analogue Scale (VAS)

Put a vertical mark (|) on the line below to show your pain experience.

No pain _____ The worst pain you can imagine

Effective date: 2017-04-13 06:29

Effective

8 Dermal Filler Effectiveness Assessments

Version: 1.0

	Title 43TW1628 Clinical Study Protocol	Doc id MA-34273
--	--	---------------------------

2017-04-13 06:29

Effective date:

Effective

Version: 1.0

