Synopsis	
Title of study: A randomised, multi-center, subject-blinded and evaluator-blinded study comparing the pain and the safety profile associated with correction of moderate to severe nasolabial folds using Restylane® Perlane lidocaine compared to Restylane® Perlane
 
Clinical Trial Number: 43TW1628
 
Countries involved, number of sites/country, number of subjects: The study will be conducted at approximately 3 sites located in Taiwan. The aim is to include 70 subjects treated with Restylane® Perlane Lidocaine (Perlane-Lido) in one nasolabial fold (NLF) and Restylane® Perlane (Perlane) in the opposite NLF, as randomly assigned.
 
Objectives:
 
Primary objective:
 
 • To evaluate the pain associated with injections of Perlane-Lido compared to Perlane for correction of moderate to severe NLFs. 
Secondary objective:
 
 • To evaluate the dermal filler effectiveness of Perlane-Lido compared to Perlane for correction of moderate to severe NLFs. 
Safety objective:
 
 • To evaluate the safety of Perlane-Lido and Perlane throughout the study. 
Endpoints:
 
Primary endpoint: Proportion of subjects that have a within-subject difference in VAS score (Perlane - Perlane-Lido) of at least 10 mm at injection.
 
Secondary endpoints:
 
 • Proportion of subjects that have a within-subject difference in VAS score (Perlane - Perlane-Lido) of at least 10 mm at 15, 30, 45 and 60 minutes after injection. • [REDACTED] • [REDACTED] • [REDACTED] • [REDACTED] 	

Effective date: 2017-04-13 06:29

Effective

Version: 1.0

 GALDERMA	Title 43TW1628 Clinical Study Protocol	Doc id MA-34273
--	--	---------------------------

	
Safety endpoints:
 
 • Incidence, intensity, duration, and onset of adverse events (AEs) collected throughout the study. • Incidence, intensity, and duration of pre-defined expected post-treatment events collected using a subject diary for 14 days after each treatment. 									

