Study Design:	
This is a randomised, multi-center, subject-blinded and evaluator-blinded study in Taiwan to evaluate the pain and the safety profile associated with correction of moderate to severe nasolabial folds using Perlane-Lido compared to Perlane. Written informed consent will be obtained before any study related procedure is performed. Subjects will be screened for eligibility within 14 days prior to study randomisation on Day 1. Subsequent to screening eligible subjects will be enrolled in the study.
 
Each subject will receive treatment on Day 1 with Perlane-Lido in one NLF and Perlane in the opposite NLF, as randomly assigned. The first injection will always start in the right NLF. No topical or local anesthetic or other pain-relieving medication, including ice, should be used before all VAS assessments are finished. The second injection, that is the injection in the left NLF, will be performed 20 ± 5 minutes after the first injection in order to reduce possible influence of immediate acute pain from the first injection on the pain perception of the second injection.
 
The subject will assess pain experienced during treatment on a 100 mm VAS scale at the end of each injection (before massaging the treatment area). The time should be recorded in the eCRF and the pain will thereafter be assessed by the subject at 15 ± 3, 30 ± 3, 45 ± 3, and 60 ± 3 minutes on the VAS after the injection on the right and left NLF, respectively. Pain will also be assessed by a treatment preference question. At the end of the treatment of the left NLF, immediately after VAS assessment of the pain at injection, the Subject will be asked which treatment was least painful.
 
Aesthetic improvement of the NLFs will be assessed by the subject and the Blinded Evaluator, independent of each other, [REDACTED] Severity of the NLFs will be assessed by the Blinded Evaluator [REDACTED]
 
The subjects will be provided with a diary in which to report symptoms for 14 days after treatment. [REDACTED]
									
Scheduled visits:	
 
 Visit 1	Screening	Day -14 to Day 1	
 
 Visit 2	Baseline (treatment)	Day 1	
 
 Visit 3	Follow-up/Final visit	Day 15 (after treatment)	
 
	Visit 1	Screening	Day -14 to Day 1	Visit 2	Baseline (treatment)	Day 1	Visit 3	Follow-up/Final visit	Day 15 (after treatment)
Visit 1	Screening	Day -14 to Day 1								

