Reference therapy:	
Restylane® Perlane (Perlane)
 
Perlane consists of stabilized hyaluronic acid of non-animal origin at a concentration of 20 mg/mL, in phosphate buffered saline. The study product is supplied in sterile 1 mL syringes with sterile contents, using a 29G thin walled (TW) x ½" needle.
 
The Treating Investigator will check the randomisation via the eCRF system, for study product i.e. the NLF on one side of the face will be randomly assigned to treatment with Perlane Lido and the opposite NLF to treatment with Perlane.
 
Perlane should be injected into the deep layer of the dermis and/or the surface layer of the subcutis of the facial skin in the NLF. The injection procedure should strictly follow the rules of aseptic surgical technique.
 
For treatment, it is recommended not to use more than 2 mL for each NLF.
 
The injection technique and the depth of injection should be the same for both sides of the face in any one subject to limit variability due to technique. Sufficient amounts of product should be injected to fully correct the defect. Defects should be fully corrected, but not overcorrected.
 
No topical or local anaesthetic or other pain-relieving medication, including ice, should be used before all VAS assessment finished.

Duration of treatment and follow-up:	
A subject will be involved in the study for up to 31 days including an up to 14 days screening period, treatment on Day 1, and 14 (+3) days follow up.

Assessments:	
Pain assessment by Visual Analogue Scale (VAS):
 
The VAS is a subjective scale to measure pain intensity. The subject shall be instructed to put a vertical mark, approximating the pain experienced during the procedure, on a 100 mm horizontal line labelled "no pain" at the left end and "the worst pain you can imagine" at the right end. The distance in mm from the left end (no pain) to the subject's VAS mark shall be measured with a standard ruler. Each NLF will be evaluated independently.
 
Subjects will evaluate injection site pain for each side of the face at the time of injection (before massaging) and at 15, 30, 45, and 60 minutes post-treatment by completing a VAS.
 
Visual Analogue Scale (VAS)
 
Put a vertical mark () on the line below to show your pain experience.
 
No pain _____ The worst pain you can imagine _____

Effective date: 2017-04-13 06:29

Effective

Version: 1.0

2017-04-13 06:29

Effective

Version: 1.0

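### The single VAS instruction refers to pain during the procedure; this suits the at-injection rating but, read literally, asks for recalled injection pain at 15, 30, 45 and 60 minutes

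*Protocol*

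**What the plan says.** Protocol 7.1 prescribes what the subject is told: "The subject shall be instructed to put a vertical mark, approximating the pain experienced during the procedure". The next paragraph of 7.1 begins "Subjects will evaluate injection site pain for each side of the face at the time of injection" and goes on to list 15, 30, 45 and 60 minutes post-treatment for the same scale. The synopsis (Assessments) and SAP 1.3.1 contain the same instruction, "approximating the pain experienced during the procedure", followed by the same five times. No visible text gives a second instruction, or a reference period, for the four later ratings.

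Three other pieces of text bear on the point:

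- The synopsis (Study Design) separates the two kinds of rating. It first says "The subject will assess pain experienced during treatment on a 100 mm VAS scale at the end of each injection", a sentence that Protocol 4.1 repeats. It then says "the pain will thereafter be assessed by the subject at 15 ± 3" minutes, and likewise at 30, 45 and 60 minutes.
- The prompt printed with the scale in Protocol 7.1 asks the subject to put a mark "on the line below to show your pain experience". It names no period.
- Protocol 7.1 adds "Each NLF will be evaluated independently".

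The later ratings feed the secondary endpoint in the synopsis and SAP 1.5.2, the proportion of subjects with a within-subject difference "of at least 10 mm at 15, 30, 45 and 60 minutes after injection". SAP 2.4.4 analyses them in Tables 9-1 to 9-3 and Graph 9-1.

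**The concern.** A pain rating means little without its reference period. At the end of an injection, pain during the procedure and pain being reported now are nearly the same thing, so the instruction works. Half an hour later they are different quantities: one is a memory of the injection, the other is residual pain. The secondary endpoint concerns the second.

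If staff gave the instruction as written at every time point, some subjects might simply re-mark their injection pain. The later ratings would then partly repeat the first one, and the tables would not describe how pain develops over the hour after injection. At stake is the description of whether any difference between the products lasts beyond the injection itself.

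**Working it through.** The documents state no figure to reproduce, so the check sets the text side by side, counts which results are exposed, and works out the direction of a possible bias.

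**Step 1: instruction against time point.**

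| Rating | Instruction (7.1, synopsis, SAP 1.3.1) | Quantity the endpoint needs | Match |
|---|---|---|---|
| At end of injection | Pain during the procedure | Pain at injection | Yes |
| 15, 30, 45, 60 min | Same sentence | Pain at that time after injection | Not if read literally |

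**Step 2: does other visible text settle the period?** The synopsis design text ties pain during treatment to the end of each injection and treats the later ratings as a continuation. Protocol 7.1 speaks of injection site pain at the later times. Both point to current pain, but neither states it as an instruction to the subject. The printed prompt is neutral: it does not contain the problem phrase and does not supply a period. The sentence on independent evaluation settles which fold is rated, not which period.

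**Step 3: which results are exposed.** Inputs: 2 folds and 5 rating times (Protocol 7.1), 70 subjects (Protocol 4.2).

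- Ratings per subject: 2 × 5 = 10, of which 2 × 4 = 8 come after injection.
- In 70 subjects: 70 × 10 = 700 ratings; 70 × 8 = 560 later and 70 × 2 = 140 at injection.
- Within-subject differences: 70 × 5 = 350, of which 70 × 4 = 280 are later.

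In the tables, these are all four post-injection proportions in Table 9-1 and four of the five time points in Tables 9-2 and 9-3. The counts show how far the wording reaches. They say nothing about how many ratings would actually be distorted.

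**Step 4: direction.** Assume that a share *p* of subjects answers literally for both folds and re-marks the injection pain exactly, while the rest rate current pain. Write *d0* for the difference (Perlane minus Perlane-Lido) at injection and *dt* for the true difference at time *t*. Then

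bias in the mean difference at *t* = *p* × (average of *d0* − *dt* among the literal responders).

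In the same way, the bias in the proportion reaching 10 mm is *p* × (proportion at injection − true proportion at *t*), both among those subjects. Three things follow:

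- The bias is zero if *p* = 0.
- It is also zero if the difference has not changed since injection.
- It overstates lasting benefit only if the at-injection difference favours Perlane-Lido and is larger than the true later difference.

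The documents give no value for *p*, *d0* or *dt*, so no size is computed and no share is assumed.

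**The case against.** The strongest reply is that the documents, read as a whole, already convey the intended meaning. Repeated timed ratings of injection site pain, described as following on from the at-injection rating and feeding endpoints defined at those times, are naturally ratings of current pain. The criticised sentence describes what staff should convey; it is not a script. The text the subject sees on the form does not contain the phrase, so harm depends on staff giving the sentence as written at the later times, and no visible text tells them to do that.

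The answer may also lie in text that cannot be seen. Protocol 4.1 breaks off just where the synopsis has its sentence on the 15 to 60 minute ratings, 4.8 and 6.6 are redacted, and the flow chart of VAS assessment is not shown. The plan cannot be faulted for what was removed.

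Much of this stands. It rules out two inferences a reader might draw. One is that the trial sets out to collect recalled pain, or will collect wrong data, at 15 to 60 minutes; the visible context points the other way. The other is that the plan nowhere states the period; that cannot be known from the public text.

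What remains is a visible instruction, given in three places, whose literal wording does not match four of its five uses. The neutral prompt cannot correct it, because it states no period either. If hidden text does state the period, the instruction still needs to be reconciled with it.

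**Conclusion.** The point holds as a wording mismatch of low severity. One instruction serves five ratings per fold; it fits the first and is ambiguous, or literally mismatched, for the other four.

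The size of any effect is unknown and may be zero. The conclusion that bias is possible rests on some subjects being given the instruction literally at the later times and following it, which the documents neither show nor exclude. The direction is conditional on the at-injection difference, as set out in the working.

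Two stronger readings should be set aside. A reader might take 560 of 700 ratings as the share of pain data that is compromised; it is only the number of ratings to which the wording applies after injection. A reader might also extend the doubt to the primary result. The documents do not support that: the primary endpoint uses the at-injection rating, for which the instruction is apt, and the 50% criterion in SAP 2.4.3 applies to that time alone. The results at 15 to 60 minutes are secondary and are reported descriptively or as proportions with confidence intervals. No visible success criterion depends on them.

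**What to change.** State the reference period by time point in the synopsis (Assessments), Protocol 7.1, SAP 1.3.1 and on the VAS form:

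- at the end of each injection: *pain in this fold during this injection*;
- at 15, 30, 45 and 60 minutes: *pain in this fold right now*.

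If a redacted section already defines the period, bring the three instruction sentences into line with it. If forms are already in use, record the wording actually given to subjects and footnote it on Tables 9-1 to 9-3, so that the later results are read accordingly.

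The cost is one line in three sections and on the form. No assessment, analysis or sample size changes. The one drawback is slightly less word-for-word comparability with any earlier study that used the present wording.
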